7.3. Method of Assignment to Treatment

Patients who meet all criteria for enrollment will be assigned to receive LY3076226. Before each patient's enrollment into the study, an eligibility check must be conducted between the investigational site and the Lilly clinical research personnel to confirm that each patient meets all enrollment criteria. Upon confirmation of eligibility, the sponsor will confirm the dose and identification number assignment and cohort for each patient. No dose escalations (that is, to the next cohort) can occur without prior discussion and agreement with the responsible Lilly CRP/CRS.

If investigators have eligible patients who have consented concurrently, more than the minimum number of patients for a cohort (1 or 3) may be entered at a particular dose level if accrual has not ceased due to excessive toxicity. This enrollment procedure is allowed because of the advanced disease state of this patient population and the screening involved in defining eligibility. This event should be approved by the sponsor following discussions with the investigators.

7.4. Blinding

This is an open-label study.

7.5. Concomitant Therapy

In the absence of clinical experience with LY3076226, patients should be closely evaluated to ensure identification of exacerbations of known side effects of concomitant medications. These should be reported immediately to the sponsor.

No other chemotherapy, radiotherapy, immunotherapy, cancer-related hormone therapy, or experimental drugs will be permitted while the patients are on this study. The need for any form of radiotherapy (including palliative) will be cause for early discontinuation from the study. In addition, any disease progression requiring other forms of specific antitumor therapy will also necessitate early discontinuation from the study. Appropriate documentation for all forms of premedications, supportive care, and concomitant medications must be captured on the CRF. Replacement hormonal therapy will be allowed. Patients on stable doses of bisphosphonates are allowed to continue.

Concomitant use of strong CYP3A4 inhibitors (for example, ketoconazole, itraconazole, clarithromycin, atazanavir, indinavir, nefazodone, nelfinavir, ritonavir, saquinavir, telithromycin, and voriconazole) with LY3076226 should be avoided due to the potential for an increase in DM4 exposure and toxicity. Where possible, consider an alternate medication with no or minimal potential to inhibit CYP3A4. Concomitant use of strong CYP3A4 inducers (for example, avasimibe [not commercially available], carbamazepine, phenytoin, rifampin, and St. John's wort) with LY3076226 should be avoided due to the potential for a decrease in DM4 exposure and potentially efficacy. Where possible, consider an alternate medication with no or minimal potential to induce CYP3A4. Concomitant use of strong CYP2D6 inhibitors (for example, bupropion, fluoxetine, paroxetine, and quinidine) with LY3076226 should be avoided

due to the potential for an increase in DM4 exposure and toxicity. Where possible, consider an alternate medication with no or minimal potential to inhibit CYP2D6. Refer to the Food and Drug Administration (FDA) website for a complete list (<http://www.fda.gov/Drugs/DevelopmentApprovalProcess/DevelopmentResources/DrugInteractionsLabeling/ucm093664.htm>).

Patients should receive full supportive care with the exception that the routine use of granulocyte colony-stimulating factor (G-CSF) is not permitted during this study. Patients should not receive G-CSF prophylactically in any cycle. G-CSF may only be used for patients who have ANC $<0.5 \times 10^9/L$, neutropenic fever, or documented infections while neutropenic. G-CSF must be discontinued at least 24 hours before the start of the next cycle of treatment. Should the use of hematopoietic colony-stimulating factors (CSFs) be necessary, follow the American Society of Clinical Oncology (ASCO) recommendations for the use of CSFs (Smith et al. 2006). If clinically indicated at any time during the study, erythropoietin and packed red blood cell transfusions may be used according to ASCO guidelines (Rizzo et al. 2010).

Premedication is not permitted for the initial dose of LY3076226 for each patient. Appropriate treatment with topical/oral corticosteroids and/or antibiotics may be instituted at the discretion of the investigator if skin reaction occurs.

All concomitant medications, including premedications, should be recorded throughout the patient's participation in the study.

7.6. Treatment Compliance

LY3076226 will be administered IV at the investigational site, under the direction of the investigator. As a result, a patient's compliance with study drug administration is ensured. Patients should attend scheduled clinic visits and must comply with study criteria under their control. Deviation(s) from the prescribed dosage regimen should be recorded on the CRF.

7.6.1. Evaluable Patients

Patients who withdraw from the study before receiving study drug will be replaced and will not be included in the safety or efficacy assessments. Safety analyses will be conducted on all patients who have received at least one dose of study drug, regardless of whether they are deemed evaluable for the assessment of a dose level.

Any patient who is discontinued from the study before completing one cycle of LY3076226 treatment may be deemed non-evaluable for assessment of a dose level, unless they experience a DLT prior to withdrawal.

Patients who receive LY3076226 on Cycle 1, Day 1 (C1D1) but discontinue from study treatment before the end of Cycle 1 will be considered evaluable for the assessment of a dose level provided it can be documented if the patient experienced a DLT within 21 days of C1D1.

Nonevaluable patients may be replaced to ensure that enough patients complete one cycle of therapy at each dose level, unless accrual to that cohort has stopped due to a DLT.

Patients who are not evaluable for PK, but who complete one cycle of therapy, may be replaced upon consultation with the investigator(s) and the Lilly CRP/CRS to ensure adequate PK data, unless accrual to that cohort has stopped due to a DLT.

8. Safety, Pharmacokinetic, Pharmacodynamic, and Efficacy Data Collection

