7.2.1. Dosing Schedule

For doses \leq 250 mg, LY3076226 will be administered as an IV infusion over approximately 60 minutes on Day 1 of each 21-day cycle. The sponsor may instruct the sites to extend the infusion time for up to 2 hours for doses greater than 250 mg. The assigned dose and duration of infusion of LY3076226 will be provided by the sponsor on a patient registration form. Subsequent doses should be adjusted as described in Section [7.2.6](#).

Premedication is not permitted for the initial dose of LY3076226 for each patient so that any observed toxicities may be appropriately characterized.

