Grade 2	First occurrence	Stop LY3076226 infusion. Administer diphenhydramine hydrochloride and acetaminophen for fever. Supply oxygen. Resume infusion at 50% of previous rate once the infusion-related reaction has resolved or decreased to Grade 1 in severity, and monitor closely for any worsening. For subsequent infusions, premedicate with diphenhydramine hydrochloride; additional premedication may be administered at the investigator's discretion. The reduced rate should be used for all subsequent infusions.
Grade 1 or 2	Second occurrence	Administer dexamethasone.
Grade ≥ 3		Stop LY3076226 infusion and disconnect infusion tubing from the patient. Administer diphenhydramine hydrochloride, dexamethasone, bronchodilators for bronchospasm, and other medications/treatment as medically indicated. Patients must not receive any further LY3076226 treatment.
Other Toxicities		
Grade ≥ 3	First occurrence	Delay LY3076226 treatment until Grade ≤ 1 or baseline following the rules in Section 7.2.6.1. Based on the investigator's discretion, the full dose of LY3076226 may be administered or the dose may be reduced to the next lowest dose level. If the event recurs at the same grade, then dose reduce LY3076226 to the next lowest dose level.
Grade ≥ 3	Second occurrence	Delay LY3076226 treatment until Grade ≤ 1 or baseline following the rules in Section 7.2.6.1. Dose reduce LY3076226 to the next lowest dose level.

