6.2. Handling of Dropouts or Missing Data

Missing data, except dates, will not be imputed. Historical data such as historical diagnosis, historical illness, pre-existing conditions and prior therapies should be collected in a sufficiently informative way. For example, in order to be considered as historical illness, events occurring in the same year as study entry should have at least a known month and year for the end date, while events occurring in previous years should have at least a known year for the end date. When dates need to be imputed, missing days will be replaced with 15th of the month and missing day/month with 01 JULY.

Patients who withdraw from the study before receiving study drug will be replaced and will not be included in the safety or efficacy assessments unless the withdrawal is due to a safety issue that is possibly related to study procedure.

In the following situations, patients will be considered non-evaluable and may be replaced to ensure that enough patients complete one cycle of therapy at each dose level, unless accrual to that cohort has stopped due to a DLT:

1. Any patient who is discontinued from the study before completing one cycle of therapy unless they experience a DLT prior to withdrawal.
2. Patients who are not evaluable for PK, but who complete one cycle of therapy.

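### DLT evaluability carries no condition on how much of the single Cycle 1 infusion was given, so a partial dose without a DLT can count as a non-event at its dose level

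*Protocol*

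**What the plan says.** LY3076226 is infused "on Day 1 of each 21-day cycle" (Protocol 7.2.1), so the DLT window contains one infusion and a Day 1 shortfall is not made up within it.

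Three rules bear on whether a patient counts for a dose level:

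- Protocol 7.6.1, leaving the study before one cycle is complete: the patient "may be deemed non-evaluable for assessment of a dose level, unless they experience a DLT prior to withdrawal".
- Protocol 7.6.1, stopping treatment: patients dosed on C1D1 who "discontinue from study treatment before the end of Cycle 1 will be considered evaluable for the assessment of a dose level". One condition is attached, and it concerns follow-up alone: DLT status over the 21 days must be documented.
- SAP 6.2 lists as non-evaluable "Any patient who is discontinued from the study before completing one cycle of therapy unless they experience a DLT prior to withdrawal". It has no route based on 21-day documentation.

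None of them mentions the amount infused. On incomplete dosing, Protocol 7.6 says only: "Deviation(s) from the prescribed dosage regimen should be recorded on the CRF".

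An interrupted infusion is foreseeable. For a Grade 2 infusion reaction, Table JOBA.4 stops the infusion and then says "Resume infusion at 50% of previous rate once the infusion-related reaction has resolved or decreased to Grade 1 in severity". It does not say how a patient who is never restarted is scored. Protocol 7.2.1 adds: "Premedication is not permitted for the initial dose of LY3076226 for each patient".

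**The concern.** The 21-day condition in 7.6.1 secures follow-up, not exposure. A patient whose Grade 2 reaction does not settle, who declines to restart, or whose line fails has had part of the dose. If no DLT follows, that patient occupies one of the 3 to 6 places in the cohort as a non-event. Where treatment then stops, 7.6.1 makes the patient evaluable. Where the patient goes on to complete Cycle 1, no dose-based exclusion applies.

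Protocol 7.2.2.1 defines the MTD by the DLT probability at doses tested, and 7.2.2.3 bases escalation on the observed DLT rate together with the model. Non-events from partial doses lower that rate at the level concerned. For those patients the error runs toward a higher MTD, which limits the RP2D, the primary objective.

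**Working it through.** **Inputs.** True DLT rates at 1.6, 2.4, 3.2, 4 and 5 mg/kg (Attachment 10, Table 2): Scenario 3, 0.10, 0.15, 0.20, 0.30, 0.42; Scenario 4, 0.13, 0.19, 0.245, 0.30, 0.38. The true MTD is 4 mg/kg in both, so over-selection means selecting 5 mg/kg. Scenarios 1 and 2 have their MTD at the top dose, so over-selection is zero there by construction.

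**Step 1: reproduce the plan's 3+3 figure.** The chance that a dose with DLT rate p passes is (1-p)^3 + 3p(1-p)^2(1-p)^3. Selecting 5 mg/kg needs all five doses to pass.

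- Scenario 3: 0.906 x 0.814 x 0.709 x 0.494 x 0.278 = 0.072. Table 3 states 0.083.
- Scenario 4: 0.853 x 0.730 x 0.611 x 0.494 x 0.343 = 0.064. Table 3 states 0.071.

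Both agree within the noise of 1000 simulations.

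**Step 2: add partial doses.** The documents give no rate, so assume a fraction q of patients receives a fraction f of the dose and is counted at the assigned level. Their risk is read off the scenario's own curve (linear between doses, proportional below 1.6 mg/kg). The apparent rate is p' = (1-q)p(d) + q p(fd). Example, Scenario 3 at 5 mg/kg with q = 0.10 and f = 0.5: 0.9 x 0.42 + 0.1 x 0.156 = 0.394. Putting p' into Step 1 gives the rate of selecting above the true MTD:

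| q (assumed) | Scenario 3, f from 0.75 to 0.25 | Scenario 4, f from 0.75 to 0.25 |
|---|---|---|
| 0 | 0.072 | 0.064 |
| 5% | 0.078-0.086 | 0.068-0.077 |
| 10% | 0.084-0.103 | 0.072-0.091 |
| 20% | 0.098-0.145 | 0.081-0.126 |

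At 5-10% the rise is about 0.4 to 3 points; at 20% it reaches about 7. Replacing partial doses restores 0.072 and 0.064.

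**Step 3: one cohort.** Suppose one of the first three patients at 5 mg/kg gets half the dose, with risk h = 0.156 (Scenario 3) or 0.197 (Scenario 4). The pass probability is (1-p)^2(1-h) + [2p(1-p)(1-h) + h(1-p)^2](1-p)^3. It rises from 0.278 to 0.374 in Scenario 3 and from 0.343 to 0.417 in Scenario 4.

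**Step 4: the model recommendation.** The posterior was computed on a grid from the stated prior on (alpha, log beta): means -0.69 and 0.39, SDs 1.95 and 1.05, correlation -0.25, reference dose 5 mg/kg. Doses with overdose probability above 0.25 are excluded. The first two cohorts on the listed ladder are taken as 0/3 at 1.6 and 0/3 at 2.4 mg/kg.

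| Data at 3.2 mg/kg | Overdose probability at 3.2 | Recommendation |
|---|---|---|
| 1/3 (partial dose counted) | 0.113 | 3.2 |
| 1/2 (partial dose dropped) | 0.162 | 3.2 |
| 2/3 (replaced, replacement has a DLT) | 0.366 | 2.4 |

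If the replacement has no DLT, the count is again 1/3 and nothing changes. If 2.4 mg/kg is skipped, 1/3 gives 0.229 (stay at 3.2) and 1/2 gives 0.324 (move to 2.4).

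**The case against.** A reader might infer that 7.6.1 biases the MTD upward in general. The documents do not support that. The permanent infusion stop that Table JOBA.4 names is for Grade 3 or higher reactions. If at least possibly related, these are DLTs under 7.2.2.1, which has no exception for them. If an assumed 5% or 10% of patients had such a reaction, over-selection would fall from 0.072 to 0.037 or 0.018 (Scenario 3) and from 0.064 to 0.032 or 0.015 (Scenario 4). Those events are correctly scored and do not cancel the misclassified non-events, but they confine the problem to DLT-free partial doses.

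A reader might also take 0.229 against 0.324 as proof that one patient decides the escalation. That holds only when 2.4 mg/kg is skipped. The 100% increment cap allows the skip, but Table JOBA.3 lists 2.4. Also, 1/2 is only the interim count, since the patient may be replaced.

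Nor do the documents say that the model scores such a patient at the full assigned dose. Attachment 10 calls its dose variable the true dose without saying whether that is planned or received.

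Other provisions narrow the gap. Related toxicity forcing withdrawal in Cycle 1 can be deemed a DLT. SAP 6.2 excludes DLT-free patients who leave the study in Cycle 1. It also lists patients not evaluable for PK, but SAP 6.3 ties PK analysis to sufficient samples, not to dose delivered. Investigators and the sponsor see the dosing record and any available PK, may depart from the model, and must document undescribed situations in writing. All of this stands. None of it says how a DLT-free partial dose is scored, and the withdrawal criterion cannot reach a line failure or a refusal.

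**Conclusion.** The point holds as a gap in the definition of DLT evaluability. 7.6.1 counts a patient who received any drug on C1D1, stopped treatment and has 21-day DLT status documented. A DLT-free patient who completes Cycle 1 after a partial infusion is not excluded on dose grounds. Both lower the observed DLT rate at the level. The two documents also disagree: for a DLT-free patient who leaves the study in Cycle 1 the protocol leaves non-evaluability optional, while the SAP makes it the rule and omits the 21-day route.

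The likely size is modest: about 0.4 to 3 points more over-selection if 5-10% of patients receive 25-75% of the dose. This rests on an assumed frequency, on the scenario curves, on counting at the assigned level, and on a plain 3+3 as proxy for the modified design. The full toxicity-band results could not be reproduced because the simulator settings are not given. A single patient changes the model recommendation only on some paths.

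**What to change.** In Protocol 7.6.1 and SAP 6.2, define a patient as DLT-evaluable if he or she either had a DLT, or received at least a sponsor-prespecified share of the planned C1D1 dose and was followed through the 21-day window. Treat other DLT-free patients as non-evaluable, replace them under the existing rule, and keep them in the safety population. Use the same wording in both documents so that leaving the study and stopping treatment are handled consistently. State in Attachment 10 whether the model uses planned or received dose.

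The cost is a short amendment to each document and an occasional replacement patient, which 7.6.1 already allows. No dose or management rule changes.

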8.1. Safety Evaluations

The safety and tolerability of LY3076226 has been assessed in nonclinical toxicology studies and the results from these studies are detailed in the IB. This Phase 1 study contains detailed safety monitoring that will permit initial characterization of the safety profile of LY3076226 in patients. Study procedures and their timing, including collection of blood and urine samples, are described in the Study Schedule ([Attachment 1](#)).

Standard laboratory tests, including chemistry, hematology, coagulation and urinalysis panels, will be performed. A serum pregnancy test will be administered if applicable. Other clinical laboratory tests will also be collected. [Attachment 2](#) lists the specific tests that will be performed for this study.

8.1.1. Safety Data Collection and Review

Investigators are responsible for monitoring the safety of patients who have entered into this study and for alerting Lilly or its designee to any event that seems unusual, even if this event may be considered an unanticipated benefit to the patient.

The investigator is responsible for the appropriate medical care of the patient during the study.

The investigator remains responsible for following, through an appropriate health care option, AEs that are serious, considered related to study treatment or the study, or that caused the patient to discontinue before completing the study. The patient should be followed until the event is resolved, the event is no longer considered to be drug-related, the event becomes stable or returns to baseline, a new treatment is initiated for the patient, or the patient dies or is lost to follow-up. Frequency of AE and SAE follow-up evaluation is left to the discretion of the investigator.

The timing of all safety evaluations is shown in the Study Schedule ([Attachment 1](#)). [Table JOBA.5](#) presents a summary of AE and SAE reporting guidelines. [Table JOBA.5](#) also shows which database or system is used to store AE and SAE data.

8.1.2. Adverse Events

Lilly has standards for reporting AEs that are to be followed regardless of applicable regulatory requirements that may be less stringent. A clinical study AE is any untoward medical occurrence in a patient or clinical investigation subject administered a pharmaceutical product and which does not necessarily have a causal relationship with this treatment. An AE can therefore be any unfavorable and unintended sign (including an abnormal laboratory finding), symptom, or disease temporally associated with the use of medicinal (investigational) product, whether or not related to the medicinal (investigational) product. Any clinically significant findings from labs, vital sign measurements, and so on, that occur should also be reported to Lilly or its designee as an AE. Lack of drug effect is not an AE in clinical studies because the purpose of the clinical study is to establish drug effect.

The investigator, monitor, and sponsor will review the collected data regularly for evidence of AEs. All patients will be assessed routinely for AEs as outlined in the study schedule. All AEs observed will be graded using CTCAE v 4.0.

The National Cancer Institute (NCI)-CTCAE v 4.0 will serve as the reference document for choosing appropriate terminology for, and grading the severity of, all AEs and other symptoms. All AEs observed will be graded using CTCAE v 4.0. Any minor version of CTCAE v 4.0 (for example, version 4.0X) may be used for this study. Minor CTCAE v 4.0 updates from the NCI will not necessitate a protocol amendment. For AEs without matching terminology within the NCI-CTCAE v 4.0 criteria, the investigator will be responsible for selecting the appropriate system organ class and assessing severity grade based on the intensity of the event. Note that both CTCAE term (actual or coded) and severity grade must be selected by study site personnel and collected on the CRF. This collection is in addition to verbatim text used to describe the AE.

In addition to collecting the AE verbatim, the CTCAE term, and the CTCAE severity grade, AE verbatim text will also be mapped by the sponsor or designee to corresponding terminology within the Medical Dictionary for Regulatory Activities (MedDRA) dictionary.

Cases of pregnancy that occur during maternal or paternal exposures to study drug should be reported. Data on fetal outcome and breastfeeding should be collected, if feasible, for regulatory reporting and drug safety evaluation.

Upon documentation of pregnancy, the patient must be removed from the study and treatment with study drug must be stopped immediately.

For all enrolled patients, study site personnel will record the occurrence and nature of each patient's preexisting conditions, including clinically significant signs and symptoms of the disease under treatment in the study. While the patient is on study, site personnel will record any change in these preexisting condition(s) and the occurrence and nature of any AEs. In addition all AEs related to protocol procedures are reported to Lilly or designee.

If a patient's dosage is reduced or treatment is discontinued as a result of an AE, study site personnel must clearly report to Lilly or its designee via electronic data entry the circumstances and data leading to any such dosage reduction or discontinuation of treatment.

Investigators will be instructed to report to Lilly or its designee their assessment of the potential relatedness of each AE to protocol procedure and/or study drug via electronic data entry.

The investigator decides whether he or she interprets the observed AEs as either related to disease, to the study medication, study procedure, or other concomitant treatment or pathologies. To assess the relationship of the AE to the study drug, the following terminologies are defined:

- **Related:** a direct cause and effect relationship between the study treatment and the AE is likely.
- **Possibly related:** a cause and effect relationship between the study treatment and the AE has not been demonstrated at this time and is not probable, but is also not impossible.
- **Unrelated:** without question, the AE is definitely not associated with the study treatment.

As per Lilly's standard operating procedures, all "related" and "possibly related" AEs and SAEs will be defined as related to study drug.

